4.15. Subject Accountability

Subject disposition will be summarized for all randomized Subjects. The number and percentage of Subjects in the following categories will be presented by treatment arm and overall:

- Subjects randomized;
- Subjects randomized and not treated;
- Subjects treated;
- Subjects with 24 hour follow-up visit, Day 5-7/Discharge, Day30, and Day 90;
- Subjects completed the study;
- Subjects discontinued from the study.

Treatment arms will be compared for the incidence and reason for study termination using counts and percentages. A summary of Subject status at the end of the study period, i.e., completed follow-up (to study end date or death) or lost to follow-up (LFU) will also be generated.

4.15.1. Demographics and Baseline Characteristics

Baseline data will be analyzed to assess the comparability of treatment arms. Subject demographics, clinical characteristics, key elements of past medical history, medications, pre-treatment NIHSS and Modified Rankin Scores and baseline characteristics will be summarized using descriptive statistics. Differences and risk ratios (as appropriate) between treatment arms and their 95% confidence intervals will be calculated for variables collected.

Statistical testing for differences between treatment arms will be performed by t-test assuming un-equal variances for continuous variables and Chi-squared/ Fisher's Exact test for categorical data. Unless otherwise stated, comparisons made between two arms will be performed using 2-sided tests at an $\alpha=0.05$ significance level.

Only ITT population will be employed for these data analyses.

- Age, defined as the number of years from date of birth to date of randomization (continuous)
- Gender (male, female)
- Race/ethnic origin (Caucasian, African American, Asian, Indian, Native American Indian/Alaska native, Native Hawaiian/Pacific Islander, Other)
- BMI

The incidence of pre-specified events[wake-up stroke, witnessed/un-witnessed stroke, etc.], conditions [hypertension, Heart Failure, Coronary Artery Disease, Extracranial Carotid Artery Disease, Peripheral Vascular Disease, Diabetes Mellitus, Dyslipidemia, Smoke history,

Previous Transient Ischemic Attack, Previous Ischemic Stroke, Previous Intra-cerebral Hemorrhage, Previous History of known ICAD] will be summarized in each treatment arm using counts and percentages.

4.15.2. Clinical Evaluation

National Institutes of Health Stroke Scale (NIHSS), Modified Rankin Scale (mRS), and Neuro imaging assessments will be summarized by counts and percentages for two treatment arms at Baseline, 24 Hr(-6/+24), Day5-7/Discharge, 30 days (± 14 days), and 90 days (± 14 days) post-procedure, if applicable.

4.15.3. Study Device Accountability

For the study device accountability, the number of study devices used, the number of subjects with study devices used, will be calculated and summarized.

4.15.4. Analysis of Primary Effectiveness Endpoints

The primary analysis of mRS scores for the interim and final analyses will be performed by Berry Consultants, LLC using custom code developed in Java and R software.

4.15.5. Analysis of Secondary Effectiveness Endpoints

The analysis population to prove the efficacy of the Trevo® Retriever consists of two arms: Treatment arm and Control arm. The two arms are defined as below.

- a. Treatment arm: the subjects who are randomized to the Trevo thrombectomy plus medical management.
- b. Control arm: the subjects who are randomized to the medical management alone.

The following Secondary Effectiveness Endpoints will be analyzed:

Both Arms:

Stryker Neurovascular

Document Title: DAWN™ Trial Statistical Analysis Plan

Document Number: CDM10000704

Rev: AB

- Proportion of subjects with “early response” at Day 5-7/Discharge (whichever is earlier), defined as a NIHSS drop of ≥ 10 points from baseline or NIHSS score 0 or 1 will be presented by providing the count and percentage for each treatment arm. The difference in the percentage between two arms and the 95% CI for the difference will be calculated using the normal approximation to binomial. P-values will be calculated by the Chi-squared test or Fisher’s exact test as appropriate. Relative Risk (RR) was provided as Trevo thrombectomy plus medical management / medical management.
- Difference in all-cause mortality rates between the two arms and the 95% CI for the difference will be calculated using the normal approximation to binomial. P-values will be calculated by the Chi-squared test or Fisher’s exact test as appropriate. Relative Risk (RR) was provided as Trevo thrombectomy plus medical management / medical management.
- Difference in median final infarct size at 24 (-6/+24) hours from randomization, by MRI T2/Flair or CT (if contraindicated for MR) will be presented with n, mean, median, interquartile, standard deviation, minimum, and maximum between two treatment arms. P-values will be calculated with t-test assuming un-equal variances to compare the difference between two treatment arms.
- Difference in revascularization rates at 24 (-6/+24) hours from randomization, by CT-MR core lab assessment of vessel patency on CTA/MRA between the two arms and the 95% CI for the difference will be calculated using the normal approximation to binomial. P-values will be calculated by the Chi-squared test or Fisher’s exact test as appropriate. Relative Risk (RR) was provided as Trevo thrombectomy plus medical management / medical management.

STRYKER CONFIDENTIAL - THIS DOCUMENT CONTAINS CONFIDENTIAL AND PROPRIETARY INFORMATION THAT IS THE PROPERTY OF STRYKER CORPORATION. NEITHER THIS DOCUMENT NOR THE INFORMATION HEREIN MAY BE REPRODUCED, USED, OR DISCLOSED TO ANY THIRD PARTY WITHOUT THE PRIOR WRITTEN CONSENT OF STRYKER CORPORATION

Treatment Arm Only:

Analysis of vessel reperfusion rates, by angiography measurement of modified TIC1 > 2b will be consistently reported with the count, rate and exact Clopper-Pearson 95% CI separately by post device and post procedure in treatment arm.

The enriched populations will be employed for secondary effectiveness endpoints analysis (refer to adaptive design plan in Appendix F of study protocol).

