4.2 Secondary Endpoints

Both Arms:

- 1. Comparison of the proportion of subjects with a good functional outcome at 90 days, defined as mRS 0-2, between the active and control groups.
- 2. Comparison of the proportion of subjects with "early response" at Day 5-7/Discharge (whichever is earlier), defined as a NIHSS drop of ≥10 from baseline or NIHSS score 0 or 1, between the active and control groups.
- 3. Difference in all cause mortality rates between the two groups.
- 4. Comparison of the median final infarct size at 24 (-6/+24) hours from randomization, by MRI T2/Flair or CT (if MR is contraindicated), between the active and control groups.
- 5. Difference in revascularization rates at 24 (-6/+24) hours from randomization, by CT-MR core lab assessment of vessel patency on CTA/MRA.

Treatment Arm only:

6. Analysis of vessel reperfusion rates (percentages) post device and post procedure, by angiography core lab measurement of modified TICI $\ge 2b$.

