1. OVERVIEW STATISTICAL PLAN

This document contains a detailed description of the Statistical Analysis Plan (SAP) for the data from the DWI or CTP Assessment with Clinical Mismatch in the Triage of Wake-Up and Late Presenting Strokes Undergoing Neurointervention (DAWN).

It provides specifications for the statistical analyses of the data to be prepared and presented for the purpose of demonstrating efficacy and safety to fulfill Food and Drug Administration (FDA) IDE requirements.

The structure and content of this SAP provides sufficient detail to meet the requirements identified by the FDA. This plan may be revised during the study to accommodate any study plan change request by FDA, to make changes to adapt to unexpected issues in study execution or data that affects planned analyses. The final plan will be issued prior to final data lock. Furthermore, as no analysis plan prepared in advance of the data can be definitive, the final report may contain additional tables, footnotes or statistical tests if warranted by the data obtained. The justification for any such additional analyses will be fully documented in the final report.

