2.2. Secondary Objectives

To provide evidence that endovascular reperfusion with Trevo is associated with a significant reduction in median infarct size compared to the control group at 24 (-6/+24) hours post randomization.

STRYKER CONFIDENTIAL - THIS DOCUMENT CONTAINS CONFIDENTIAL AND PROPRIETARY INFORMATION THAT IS THE PROPERTY OF STRYKER CORPORATION. NEITHER THIS DOCUMENT NOR THE INFORMATION HEREIN MAY BE REPRODUCED, USED, OR DISCLOSED TO ANY THIRD PARTY WITHOUT THE PRIOR WRITTEN CONSENT OF STRYKER CORPORATION

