3.1.2. Secondary Endpoints

Both Arms:

1. Proportion of subjects with “early response” at Day 5-7/Discharge (whichever is earlier), defined as a NIHSS drop of ≥ 10 points from baseline or NIHSS score 0 or 1
2. Proportion of subjects suffering all-cause mortality between the two groups.
3. Difference in median final infarct size at 24 (-6/+24) hours from randomization, by MRI T2/Flair or CT (if contraindicated for MR)
4. Proportion of revascularization rates at 24 (-6/+24) hours from randomization, by CT-MR core lab assessment of vessel patency on CTA/MRA.

Treatment Arm Only:

Analysis of vessel reperfusion rates (percentages) post device and post procedure, by angiography core lab measurement of modified TIC1 $\geq 2b$.

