4.3. The Secondary Efficacy and Safety Endpoints

For binary outcomes, the count and percentage will be provided for each treatment arm. The difference in the rate between the treatment arms and the 95% CI for the difference will be calculated using the normal approximation to binomial. P-values will be calculated by the Chi-squared test as appropriate. Fisher's exact test is used in place of the Chi-square test when at least one cell count in the 2x2 table has expected value less than 5 or total sample size is less than or equal to 40. The p-value will be denoted with an asterisk (*) in the case where a Fisher's exact test was used.

Relative Risk (RR) was provided as Trevo thrombectomy plus medical management / medical management.

$$SE = \sqrt{\{(1-p_1)/n_{11} + (1-p_2)/n_{21}\}}$$

$$95\% \text{ CI} = RR \cdot \exp(\pm 1.96 \cdot SE).$$

For continuous outcomes, n, mean, median, interquartile (Q3-Q1), standard deviation, minimum, and maximum values will be provided for each treatment arm. P-values will be calculated using a t-test assuming un-equal variances to compare the difference between two treatment arms.

Difference = Trevo thrombectomy plus medical management – medical management.

$$95\% \text{ CI} = \text{Diff} \pm 1.96 \cdot SE$$

$$SE = \sqrt{p_1q_1/n_1 + p_2q_2/n_2} \text{ for proportions,}$$

$SE = \sqrt{[(1/n_1 + 1/n_2)\{(n_1-1)s_1^2 + (n_2-1)s_2^2\}/(N-2)]}$ for continuous variables.

For ordinal variables a Wilcoxon rank sum test will be used and footnoted.

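### The secondary objective and its endpoint concern median infarct size, but the planned p-value is a t-test of means and no test or interval for the medians is planned

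*SAP*

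**What the plan says.** Protocol 3.2 and SAP 2.2 each list one secondary objective: evidence that reperfusion with Trevo "is associated with a significant reduction in median infarct size compared to the control group". The matching endpoint is on the same scale in both documents: "Comparison of the median final infarct size at 24 (-6/+24) hours from randomization" in Protocol 4.2 and "Difference in median final infarct size at 24 (-6/+24) hours from randomization" in SAP 3.1.2.

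The infarct bullet in SAP 4.15.5 opens with the difference in medians, lists summary statistics that include the mean, median and interquartile range, and then states "P-values will be calculated with t-test assuming un-equal variances to compare the difference between two treatment arms". It names no confidence interval, although the other three two-arm bullets in that section each do.

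SAP 4.3 gives the same rule for all continuous outcomes: "P-values will be calculated using a t-test assuming un-equal variances to compare the difference between two treatment arms". Its interval is the difference plus or minus 1.96 standard errors, with the standard error built from the arm standard deviations. It adds: "For ordinal variables a Wilcoxon rank sum test will be used and footnoted". The protocol names no test for infarct size.

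**The concern.** The objective claims a significant reduction in a median. The only p-value planned for it answers a question about means, and the mismatch sits inside a single SAP bullet.

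Infarct volume cannot be negative and is probably right-skewed, so its mean and median can lie well apart. If treatment changes the shape of the distribution as well as its level, a significant t-test could be reported as a reduced median when the medians are equal, or a real median difference could be missed. The t-test and a median analysis also differ in power, so the choice between them should not be made after the results are known.

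**Working it through.** **Target against method**

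| Item | Place | Scale |
|---|---|---|
| Objective | Protocol 3.2, SAP 2.2 | Median |
| Endpoint | Protocol 4.2, SAP 3.1.2 | Median |
| Descriptive output | SAP 4.15.5 | Mean and median |
| P-value | SAP 4.15.5, 4.3 | Mean |
| Interval | SAP 4.3 (generic) | Mean |
| Rank test | SAP 4.3 | Ordinal variables only |

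The plan gives no effect size, SD or power for infarct volume, so it has no figure to reproduce. What follows is illustration under assumed shapes.

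**Inputs.** Protocol 5.2.1, Table 2, shows infarct volumes of 101.2 (96.3) and 83.1 (64.6). I read the unlabelled brackets as SDs. Then SD/mean (CV) = 96.3/101.2 = 0.952 and 64.6/83.1 = 0.777, with midpoint 0.864. The table compares patients treated within and after 8 hours, so it is not a treated-versus-control contrast.

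Two families are used:
- Lognormal: log-SD = sqrt(ln(1 + CV²)) = 0.803 and 0.688.
- Gamma: shape = 1/CV² = 1.104 and 1.655.

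The t-test (unequal variances) is two-sided at 5%. SAP 4.15.1 states that level for baseline comparisons, and I assume it here. The comparator is a percentile bootstrap interval for the difference in medians (500 resamples within arm), counted when it excludes zero. There are 4,000 simulated trials per setting, so the Monte Carlo SE is at most 0.8 points. Results are given as lognormal / gamma.

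**(a) Same distribution in both arms** (mean 60 cc, CV 0.952), 75 to 250 per arm. The t-test rejects 5.0-5.5% / 5.0-5.7% and the median interval 4.4-4.5% / 4.1-4.7%. Both hold their size.

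**(b) Equal medians of 50 cc, CV 0.952 against 0.777.** The true means are 69.0 and 63.3 / 69.5 and 61.9 cc.

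| Per arm | t-test | Median interval |
|---|---|---|
| 100 | 9% / 14% | 4-5% |
| 250 | 18% / 30% | 4-5% |

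Hand check, lognormal at 100 per arm:
- SDs are 0.952 × 69.0 = 65.7 and 0.777 × 63.3 = 49.2.
- SE = sqrt((65.7² + 49.2²)/100) = 8.21.
- The standardised difference is 5.7/8.21 = 0.69.
- P(Z > 1.96 − 0.69) + P(Z < −1.96 − 0.69) is about 11%, slightly above the simulated value because the data are skewed.

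The Wilcoxon test rejects about 5% in (b). In the lognormal case this follows from the set-up: log volumes are symmetric about the same centre, so neither arm tends to be larger. It is not a general guarantee.

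**(c) Half the shape gap** (0.952 against 0.864, medians equal). The t-test rejects 6% / 7% at 100 per arm and 9% / 11% at 250.

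**(d) Pure 25% reduction** (means 60 and 45 cc, same CV of 0.952).

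| Per arm | t-test | Median interval | Loss in points |
|---|---|---|---|
| 100 | 59.1% / 54.5% | 51.7% / 29.9% | 7.4 / 24.6 |
| 150 | 75.3% / 72.5% | 70.0% / 41.8% | 5.3 / 30.7 |
| 250 | 92.2% / 91.6% | 89.3% / 65.3% | 2.9 / 26.3 |

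In a separate run of 2,000 trials of (d), Wilcoxon power was about 70% / 47% at 100 per arm and 97% / 84% at 250. It beats the t-test under the lognormal and trails it under the gamma.

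**The case against.** Several objections stand, and they limit the point.

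- **Validity.** The t-test holds its size when treatment does nothing. In (b) the true means differ, so a rejection there is not a false positive for means. A reader might infer that the planned test has an inflated error rate; setting (a) shows that it does not.
- **Likelihood.** The documents do not show that the arms will differ in shape. A reader might take Table 2 as evidence that they will, but that table contrasts treatment times. The excess shrinks in (c) and is absent without a gap.
- **Descriptive reporting.** SAP 4.15.5 can be read as planning the point difference in medians, and the two arm medians give it anyway. Only the inference is missing.
- **Status.** No alpha is allocated to secondary endpoints, and SAP 4.5 says additional endpoint analyses are supportive without alpha control. Whether that covers the listed secondary endpoints is arguable.
- **Later repair.** A reader might infer that any median analysis added from here on would be post hoc. SAP 1 does say "the final report may contain additional tables, footnotes or statistical tests if warranted by the data obtained", and a test added by that clause alone would not be pre-specified. But the same section allows the plan to be revised during the study and states "The final plan will be issued prior to final data lock", so a proper route is open.

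None of this supplies an analysis of the target that the objective names.

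**Conclusion.** The point holds as a mismatch between target and inference, and this rests on the text alone. A significant t-test would support a statement about mean infarct volume. It would support one about the median only if the arms differ by shift or scale.

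The size of the possible disagreement rests on assumed lognormal or gamma volumes with an assumed shape gap. The simulations show what can happen, not what is likely.

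A reader might go further and infer that the trial's conclusion is at risk. The documents do not support that: SAP 4.1 and 4.2 rest success on the mRS analyses alone. The mismatch should be corrected, but it does not threaten the primary result.

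**What to change.** Before data lock, by the revision route in SAP 1, name in SAP 4.15.5 one analysis as the inference for this endpoint, in the enriched population that the section already specifies. Any of three would do:

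1. **Wilcoxon rank-sum test with a Hodges-Lehmann estimate and 95% CI.** This extends the rank test already in SAP 4.3. State that it is inference on medians only under a shift assumption.
2. **Difference in medians with a bootstrap 95% CI.** This targets the median directly. For a pure 25% reduction at 100-250 per arm it gives up 3-7 power points against the t-test (lognormal) or 25-31 (gamma).
3. **Keep the t-test and restate the objective and endpoint as a mean difference** in Protocol 3.2 and 4.2 and SAP 2.2 and 3.1.2, with the summaries that repeat them. There is no power cost, but the stated target changes and the protocol must be amended.

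Under 1 or 2, keep the t-test and the SAP 4.3 interval as supportive, labelled as inference on means. Options 1 and 2 cost one sentence in SAP 4.15.5 and minor programming. No option needs new data.

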Study Objective				
Primary Objective	To evaluate the hypothesis that Trevo thrombectomy plus medical management leads to superior clinical outcomes at 90 days as compared to medical management alone in appropriately selected subjects experiencing an acute ischemic stroke when treatment is initiated within 6-24 hours after last seen well.			
Secondary Objective(s)	To provide evidence that endovascular reperfusion with Trevo is associated with a significant reduction in median infarct size compared to the control group at 24 (-6/+24) hours post randomization.			
Test Device	Trevo [®] ProVue [™] and Trevo [®] XP ProVue [™] Retrievers			
	Study Design			
Study Design	Prospective, randomized, multi-center, Phase II/III (feasibility/pivotal), adaptive, population enrichment, blinded endpoint, controlled trial.			
Planned Number of Subjects	A maximum of 500 subjects is planned to be enrolled; 250 in the Treatment arm and 250 in the Control arm. The minimum sample size is 150 subjects.			
Planned Number of Sites / Countries	Worldwide (up to 50 sites). No more than 20 sites will be outside of the U.S.			
Primary Endpoint	90-day disability assessed by the modified Rankin scale (mRS)			
Secondary Endpoints	 Proportion of subjects with a good functional outcome at 90 days, defined as mRS 0-2 Proportion of subjects with "early response" at Day 5-7/Discharge (whichever is earlier), defined as a NIHSS drop of ≥10 points from baseline or NIHSS score 0 or 1 Difference in all cause mortality rates between the two groups. Difference in median final infarct size at 24 (-6/+24) hours from randomization, by MRI T2/Flair or CT (if contraindicated for MR) Difference in revascularization rates at 24 (-6/+24) hours from randomization, by CT-MR core lab assessment of vessel patency on CTA/MRA. Treatment Arm Only: Analysis of vessel reperfusion rates (percentages) post device and post procedure, by angiography core lab measurement of modified TICI ≥ 2b 			

Document Number: CDM10000146

Rev: AD

Primary Safety Outcome	Both Arms: 1. Incidence of stroke-related mortality at 90 days					
Secondary Safety Outcomes	 Both Arms: Incidence of SICH, by ECASS III definition, within 24 (-6/+24) hours post randomization (time zero) Incidence of neurological deterioration from baseline NIHSS score through Day 5-7/discharge (whichever is earlier) post randomization (time zero). Neurological deterioration is defined as ≥ 4 point increase in the NIHSS score from the baseline score. 					

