0 - No Perfusion - No antegrade flow beyond the point of occlusion

1 - Penetration with Minimal Perfusion - The contrast material passes beyond the area of obstruction but fails to opacify the entire cerebral bed distal to the obstruction for the duration of the angiographic run

2 - Partial Perfusion - The contrast material passes beyond the obstruction and opacifies the arterial bed distal to the obstruction; However, the rate of entry of contrast into the vessel distal to the obstruction and/or its rate of clearance from the distal bed are perceptibly slower than its entry into and/or clearance from comparable areas not perfused by the previously occluded vessel, e.g., the opposite cerebral artery or the arterial bed proximal to the obstruction

2a - Only partial filling (< 50%) of the entire vascular territory is visualized

2b - Filling of \geq 50% all of the expected vascular territory is visualized, but the filling is slower than normal

3 - Complete Perfusion - Antegrade flow into the bed distal to the obstruction occurs as promptly as into the obstruction and clearance of contrast material from the involved bed is as rapid as from an uninvolved other bed of the same vessel or the opposite cerebral artery.

Document Number: CDM10000146

Rev: AD

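### SAP 4.15.5 gives the treatment-arm reperfusion cut-off as modified TICI > 2b where the endpoint is ≥ 2b; read literally, only grade 3 counts

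*SAP*

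**What the plan says.** The endpoint is defined the same way in three places:

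- Protocol synopsis: "by angiography core lab measurement of modified TICI ≥ 2b".
- Protocol 4.2: "by angiography core lab measurement of modified TICI", followed by ≥ 2b.
- SAP 3.1.2: "by angiography core lab measurement of modified TIC1", again followed by ≥ 2b.

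SAP 4.15.5 gives the analysis of this endpoint for the treatment arm: a count, a rate and an exact Clopper-Pearson 95% interval, reported separately post device and post procedure. Its criterion is "by angiography measurement of modified TIC1 > 2b". It differs from the definition in two ways: the sign is strict, and the core lab is not named.

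SAP 4.15.7 then summarises mRS 0-2 by reperfusion status, post device and post procedure, without stating a cut-off.

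**The concern.** SAP 4.15.5 is where a programmer would look for the derivation of this variable. A strict inequality there changes the endpoint from substantial-or-complete reperfusion to complete reperfusion only. The published rate would then differ from the endpoint in the protocol, under the same label.

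The change would also conflict with how the protocol treats grade 2b during the procedure. Protocol 7.4 sets success at 2b or above against failure at 0 to 2a. Protocol 7.5 lists grade 2b or 3 as a reason to end the procedure, and Protocol 7.7.1 counts grades 2b and 3 as reperfused. Under the literal SAP sentence, a subject whose procedure ended because the protocol's own criterion had been met at 2b would be reported as not reperfused.

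The summary in SAP 4.15.7 could be affected too. It gives no cut-off, and the only one in the SAP's analysis sections is the one in 4.15.5.

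**Working it through.** The plan states no expected rate, power or sample size for this endpoint, so there is no figure to reproduce. The check is an enumeration of the scale.

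**Scale.** The modified TICI scale in Protocol Appendix C has grades 0, 1, 2a, 2b and 3. Grade 2b requires filling of at least half the territory; its description ends "all of the expected vascular territory is visualized, but the filling is slower than normal". The grade above it begins "3 - Complete Perfusion - Antegrade flow into the bed distal to the obstruction occurs as promptly as into the obstruction". No grade lies between them.

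**Success set under each sign.**

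- ≥ 2b: {2b, 3}
- > 2b: {3}

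**Effect on the rate.** Let n be the number of treatment-arm subjects in the denominator, and n_2b and n_3 the numbers at grades 2b and 3.

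- As defined: (n_2b + n_3) / n
- As written in SAP 4.15.5: n_3 / n
- Difference: n_2b / n, the share of subjects at grade 2b

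The Clopper-Pearson interval would be built around n_3 / n. For the post-device rate, n_2b counts only 2b subjects not already classed as failures by the rescue-therapy rule in Protocol 7.4, since those are failures under either sign.

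**Can the share be put in numbers?** Not from the documents. The earlier series tabulated in Protocol 5.2.1 report grades 2 and 3 combined (TICI 2-3 or TIMI 2-3) and do not separate 2b from 3. As a conversion only: at the maximum treatment-arm size of 250, each 10 percentage points at grade 2b is 0.10 × 250 = 25 subjects. If the share were anywhere from 10% to 50%, which is purely an assumption, the reported rate would fall by 10 to 50 points, or 25 to 0.50 × 250 = 125 subjects.

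**Knock-on in SAP 4.15.7.** If the strict cut-off were carried over, the n_2b subjects would move from the reperfused to the non-reperfused group. The denominators of both groups would change, and the mRS 0-2 proportions could change with them.

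**Was the change deliberate?** The SAP revision table records no change to this criterion, and the protocol passages listed above all count 2b as success.

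**The case against.** The strongest objection is that the case rests on one comparison sign in text converted from PDF. A > typed with an underline could lose its lower bar, and the disputed string is visibly misread (TIC1 for TICI). Signs are unreliable elsewhere too: Protocol 5.2.5 shows the second mismatch subgroup with ≤ where Protocol 6.1 has <. This stands as a reason to check the source PDF. It does not dispose of the point. SAP 3.1.2 has the same TIC1 misreading and kept its ≥, the ≥ in the early-response item of SAP 4.15.5 is intact, and the 4.15.5 sentence is worded differently from 3.1.2.

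A second objection is that SAP 4.15.5 only analyses endpoints already defined in 3.1.2, so a careful analyst would follow the definition. That is likely, and it limits the practical risk. But the SAP has no rule on which section prevails when two disagree.

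Three stronger readings are tempting, and the documents do not support them:

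- A reader might infer that omitting the core lab lets site reads replace core-lab reads. Protocol 13.3.1 assigns the post-device and post-procedure modified TICI scores to the Angiographic Core Lab, and SAP 3.1.2 agrees. The omission is loose wording and authorises no site read.
- A reader might want to quote a specific fall in the rate by assuming an overall success rate and a split between grades 2b and 3. Neither figure is in the documents.
- A reader might suspect an effect on the trial's conclusions. This is a descriptive rate in one arm, with no between-arm test, and it plays no part in the primary analyses, the interim rules or the sample size.

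**Conclusion.** The sentence in SAP 4.15.5 is wrong as written: it contradicts SAP 3.1.2, Protocol 4.2 and the protocol synopsis. Followed literally, it counts only grade 3 and lowers both reported reperfusion rates by exactly the share of subjects at grade 2b, a share the documents do not give. The summary in SAP 4.15.7 is exposed only if it takes its cut-off from 4.15.5.

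The conclusion rests on one assumption, that the source PDF prints the sign as >. If it prints ≥, the contradiction disappears. What would remain is the missing mention of the core lab in 4.15.5 and the missing cut-off in 4.15.7. In either case this is a minor correction.

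**What to change.** Check the sign in SAP 4.15.5 against the source PDF. If it is >, replace the phrase with the protocol synopsis wording: "by angiography core lab measurement of modified TICI ≥ 2b". If it is already ≥, add only the mention of the core lab. In SAP 4.15.7, state that reperfusion status uses the same core-lab cut-off, for example by reference to SAP 3.1.2.

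The cost is one symbol, two words and a cross-reference. No design decision is involved, because the change restores the plan's own definition. SAP section 1 allows revision, with the final plan issued before data lock.
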